**--Arm 2: Supportive social incentive intervention--**

Participants in this arm will be asked to identify a family member or friend to be their support sponsor. This sponsor will be encouraged to support the participant in their progress during the study. A weekly report will be sent by email to the sponsor with the participant's performance (e.g., step goal, average step count for that week, points and level).

**--Arm 3: Competitive social incentive intervention--**

Participants in this arm will be in a group of three total participants. At the end of each week the participants will receive an email with a leaderboard that ranks them on their cumulative points in the study thus far and also displays their level. In the event there is a tie in total cumulative points, the participants will be secondarily ranked on level. This feedback may help to induce participants to compete for the top spot among the group.

**--Arm 4: Collaborative social incentive intervention--**

Participants in this arm will be in a group of three total participants as a team. Each day one of the members of the group will be randomly selected to represent their team for that day. If the participant selected met his or her step goal on the previous day, the team keeps their points. If he or she didn't meet their goal, then the team loses 10 points. In this design, each person is accountable to the others on the team and this may induce a collaborative effort to meet their daily goals. The entire team moves up a level only if the team has at least 40 points by the end of the week.

### *5.2 Study duration*

This study is anticipated to take up to 2 years to complete and includes a 24-week intervention period and 12-week follow-up period

### *5.3 Target population*

Adults age 18 years or older with a self-reported body mass index of 25 or greater, that are employees of Deloitte.

### *5.4 Accrual*

This study has been powered for two phases of hypothesis testing. In the first phase, we will compare each of the three intervention arms to control. We estimate that a sample of 600 participants allocated in a 1:1:1:1 distribution, will ensure at least 80% power to detect an 800 step difference between each intervention arm and control, with a standard deviation of 2000 steps. This calculation assumes a 10% dropout rate and a conservative Bonferroni adjustment of the type I error rate with a 2-sided alpha of 0.017. In the second phase, we will compare successful intervention arms to each other. We expect that the magnitude of difference between intervention arms will be less than that of successful intervention arms compared to control. For this second phase of analyses will use a conservative Bonferroni adjustment of the type I error rate with a 2-sided alpha of 0.017 to adjust for up to 3 comparisons. Because only intervention arms which demonstrated a significant difference with the control are compared with each other in the second phase, the overall familywise error rate of this two-phase procedure is controlled at 0.05.

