This study has been powered for two phases of hypothesis testing. In the first phase, we will compare each of the three intervention arms to control. We estimate that a sample of 600 participants allocated in a 1:1:1:1 distribution, will ensure at least 80% power to detect an 800 step difference between each intervention arm and control, with a standard deviation of 2000 steps. This calculation assumes a 10% dropout rate and a conservative Bonferroni adjustment of the type I error rate with a 2-sided alpha of 0.017. In the second phase, we will compare successful intervention arms to each other. We expect that the magnitude of difference between intervention arms will be less than that of successful intervention arms compared to control. For this second phase of analyses will use a conservative Bonferroni adjustment of the type I error rate with a 2-sided alpha of 0.017 to adjust for up to 3 comparisons. Because only intervention arms which demonstrated a significant difference with the control are compared with each other in the second phase, the overall familywise error rate of this two-phase procedure is controlled at 0.05.

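### The three phase 1 comparisons with control stay at a flat 0.017 after another arm has succeeded; a capped step-down would add power at no cost in participants, most of it if all three arms work

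*Combined protocol and SAP*

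**What the plan says.** The same testing paragraph stands in section 5.4 (Accrual) and section 9 (Analysis plan). "In the first phase, we will compare each of the three intervention arms to control". The sample size statement is "We estimate that a sample of 600 participants allocated in a 1:1:1:1 distribution, will ensure at least 80% power to detect an 800 step difference", with an SD of 2000 steps. It adds: "This calculation assumes a 10% dropout rate and a conservative Bonferroni adjustment of the type I error rate with a 2-sided alpha of 0.017". Phase 2 also uses 0.017, for up to three between-arm comparisons. Overall control at 0.05 is justified on the ground that "only intervention arms which demonstrated a significant difference with the control are compared with each other in the second phase".

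Neither section describes a step-down, or any reuse of the error rate after a rejection. The plan itself calls the adjustment conservative.

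**The concern.** Once one arm has been shown to differ from control, at most two of the three phase 1 null hypotheses can still be true. Once two have been rejected, at most one can be. Holding every comparison at 0.017 regardless therefore leaves part of the 0.05 unused in the situations the trial hopes for, where some arms work.

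Phase 1 carries the primary outcome and is also the gate to phase 2. An effective arm that narrowly misses 0.017 is recorded as unsuccessful and is then left out of every between-arm comparison.

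**Working it through.** **Inputs, all from section 5.4.** 600 participants 1:1:1:1, so 150 per arm; 10% dropout, so 150 × 0.9 = 135 evaluable per arm; difference 800 steps; SD 2000; two-sided level 0.017. Participants are treated as independent, as the plan's calculation implies.

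**The plan's own figure.** Standard error of a difference = 2000 × √(2/135) = 243.4 steps. Power = Φ(800/243.4 − 2.387) = Φ(0.900) = 81.6% (81.1% with the t distribution). Conversely, 80% power needs 2 × 2000² × (2.387 + 0.842)²/800², or 131 per arm. Then 131/0.9 gives 146 per arm and 584 in total, close to 600. The stated power reproduces.

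**Error actually used.** I simulated four arm means (135 per arm, shared control, one to two million draws) through both phases. An error is any false rejection in either phase. The effects in the table are large, because that is where the error peaks.

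| True state | Flat 0.017, phase 2 at 0.017 | Steps 0.05/3, 0.025, 0.0333, phase 2 at 0.05/3 |
|---|---|---|
| All arms equal control | 0.045 | 0.044 |
| One effective, two null | 0.032 | 0.046 to 0.047 |
| Two equal and effective, one null | 0.034 | 0.049 to 0.050 |
| Three equal and effective | 0.045 | 0.044 |

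The flat rule stays below 0.05 even though 3 × 0.017 = 0.051, because the comparisons are correlated. Its slack is in the two middle rows.

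**Why the step-down holds 0.05 whatever the correlation.** The ordered p-values are tested in turn, stopping at the first non-rejection.
- Three null arms: an error needs a p-value at or below 0.05/3, so at most 3 × 0.05/3 = 0.05.
- Two null arms: the first false rejection comes no later than the second step, so at most 2 × 0.025 = 0.05. Comparing the two null arms in phase 2 presupposes an error already made.
- One null arm, the other two equal: at most 0.0333 in phase 1 plus 0.0167 in phase 2, which is 0.05.
- Three equal effective arms: at most 3 × 0.05/3 = 0.05 in phase 2.

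The third case fixes the cap. An ordinary Holm procedure ends at 0.05, so its bound there is 0.05 + 0.017 = 0.067; the simulated value is 0.066. It is also why phase 2 should be exactly 0.05/3: 0.0333 + 0.017 = 0.0503.

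**Power, flat rule against step-down, 135 per arm.**

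| True state | Quantity | Flat | Step-down |
|---|---|---|---|
| All three arms +800 | Per-arm power | 81.6% | 86.0% |
| | All three succeed | 63.6% | about 73.6% |
| | A given pair enters phase 2 | 70.9% | about 78.7% |
| Two arms +800, one null | Power per effective arm | 81.6% | 84.0% |
| One arm +800, two null | Power for that arm | 81.6% | 81.5% |

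For scale, the flat rule reaches 85.9% per arm only with 150 evaluable per arm. That is (150 − 135) × 4/0.9, or about 67 more randomised participants.

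**Dependence on independence.** In arms 3 and 4 (section 5.1) participants interact in groups of three, while the model in section 9 names participant random effects and no group term. The documents give no intraclass correlation. I assumed 0.05 to 0.10 in those two arms, unmodelled, which inflates the variance of their means by 1 + 2 × 0.05 = 1.10 to 1 + 2 × 0.10 = 1.20. With two equal, strongly effective arms and one null, familywise error is then about 0.055 to 0.064 for the step-down, against 0.039 to 0.046 for the flat rule. With all arms null the two rules are alike, at about 0.050 to 0.056.

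**The case against.** The strongest reply is that the plan does what it promises. It claims at least 80% power per comparison and 0.05 overall, delivers both, and says openly that its adjustment is conservative. That stands. A reader might infer that the power statement or the familywise claim is wrong; the documents and the arithmetic support neither inference.

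A reader might also take 4 points per arm and 10 points for all three as the general loss. That is the case in which every arm gains 800 steps. Section 5.4 does use 800 steps for each arm, but as the difference to detect in each comparison, and the plan never makes success of all three arms a goal. With two effective arms the gain is about 2.4 points. With one there is none, and the step-down is lower by 0.1 point because 0.05/3 is slightly below 0.017.

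The benefit to phase 2 should not be oversold either. If two arms gain 800 steps and the third 400, the chance of detecting a given 400-step between-arm difference is about 1.3% under the plan and 2.3% under the step-down.

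Finally, the step-down spends slack that now gives some protection if the group structure is ignored. This also stands, and it makes sound standard errors a condition of the change. It is not a full defence of the flat rule, which can itself slightly exceed 0.05 with all arms null under the same assumption.

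**Conclusion.** The point holds as an optional efficiency gain. The flat 0.017 is stricter than the 0.05 target requires once an arm has succeeded, and a capped step-down recovers power on the primary outcome without more data. The size is 4.4 points per arm (86.0 − 81.6) and about 10 points for all three succeeding (73.6 − 63.6) if every arm gains 800 steps, falling to about 2.4 points and then to nothing as fewer arms work. These figures rest on 135 evaluable per arm, SD 2000 and independent participants. The Bonferroni argument for 0.05 needs no assumption about correlation between the tests, but it does need each test to hold its own level. With unmodelled clustering in arms 3 and 4 it does not.

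**What to change.** In sections 5.4 and 9, state that the three phase 1 p-values are ordered and tested at 0.05/3, then 0.025, then 0.0333, stopping at the first non-rejection. Set phase 2 at exactly 0.05/3 per comparison. State that the last phase 1 step is capped at 0.0333 because phase 2 shares the same 0.05, so that nobody substitutes an ordinary Holm or Hochberg procedure ending at 0.05. Make the change conditional on a primary model whose standard errors account for the three-person groups in arms 3 and 4, and settle it before any comparison by arm is seen.

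The cost is a few sentences, with no change to sample size or data collection. One drawback is in reporting: simultaneous 98.3% intervals (1 − 0.05/3) would no longer match every step-down decision, so they should be shown as conservative intervals beside adjusted p-values. The other is that the slack in the familywise error is used up.

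### The phase 2 rule is valid but spends less than the 0.05 it is allowed; a gate-aware step-down rule would add power at no cost in participants, by an amount that depends on effect sizes the plan does not give

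*Combined protocol and SAP*

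**What the plan says.** Section 5.4 and section 9 carry the same text. Phase 1 compares each of three intervention arms with control, using "a sample of 600 participants allocated in a 1:1:1:1 distribution". The stated aim is "at least 80% power to detect an 800 step difference between each intervention arm and control", "with a standard deviation of 2000 steps"; the calculation "assumes a 10% dropout rate and a conservative Bonferroni adjustment of the type I error rate with a 2-sided alpha of 0.017".

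Phase 2 is gated: "In the second phase, we will compare successful intervention arms to each other". Its level is a "conservative Bonferroni adjustment of the type I error rate with a 2-sided alpha of 0.017 to adjust for up to 3 comparisons". The claim of overall control at 0.05 rests on the fact that "only intervention arms which demonstrated a significant difference with the control are compared with each other in the second phase".

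Neither section gives a different level when fewer than three comparisons remain, or a step-down after a rejection. Neither gives a phase 2 effect size or power. They say only that differences between arms are expected to be smaller than differences from control.

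**The concern.** The 0.017 is sized for three comparisons, but the gate often leaves fewer. If exactly two arms succeed there is one comparison, and it is still charged as one of three. If all three succeed and one equality is rejected, the other two cannot both be true (that would make all three arms equal), yet each is still held to 0.017.

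In both situations part of the 0.05 is left unused. Phase 2 is where the plan expects the smaller differences and so has the least power. A rule that uses the spare error rate would help there without recruiting anyone.

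**Working it through.** **Inputs from section 5.4.** 600 participants, 150 per arm; 10% dropout, so 0.9 × 150 = 135 evaluable per arm; SD 2000; two-sided 0.017; 800 steps versus control. **Assumptions.** Participants are independent, tests are two-sided z tests, and the arm effects are as listed below, because the documents give none for phase 2.

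**The plan's own figure.** n per arm = 2(z₀.₀₁₇ + z₀.₈₀)² × SD²/Δ² = 2(2.387 + 0.842)² × 2000²/800² = 130.3, so 131. Dividing by 0.9 gives 146 per arm and 584 in total; 600 covers this. With 135 per arm the standard error of a difference is 2000 × √(2/135) = 243.4, and power is Φ(800/243.4 − 2.387) = Φ(0.900) = 81.6%. The stated 80% is reproduced.

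**What level is available.**
- *One ineffective arm, two equally effective arms.* The ineffective arm uses 0.0167 in phase 1. That leaves 0.05 − 0.0167 = 0.0333 for the single pair.
- *Three successful arms, one equality false.* At most one other equality can be true, so after a first rejection at 0.05/3 the other two can be tested at 0.05 (Shaffer step-down).
- *All arms null.* At most 3 × 0.0167 = 0.05 in phase 1; a phase 2 error needs a phase 1 error first.
- *Two null arms.* At most 2 × 0.0167 = 0.0333.
- *Three equal effective arms.* No simple sum covers the case where only two of them pass, so this rests on simulation.

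**Familywise error, simulated** (1,000,000 runs per pattern; Monte Carlo SE about 0.0002 near 0.05). Effects are steps over control.

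| True effects | Plan | Modified rule |
|---|---|---|
| 0/0/0 | 0.045 | 0.044 |
| 0/2000/2000 | 0.033 | 0.049 |
| 0/0/2000 | 0.032 | 0.031 |
| 800/800/800 | 0.014 | 0.014 |
| 1500/1500/1500 | 0.045 | 0.044 |
| 1200/2000/2000 | 0.017 | 0.049 |

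The second and last rows show the unspent error. The highest value for the modified rule in any run was 0.0504, which agrees with the bound of 0.05 within simulation error.

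**Power of one comparison once exactly two arms have succeeded** (gate ignored), Φ(Δ/243.4 − z) plus the negligible opposite tail, with z = 2.387 at 0.017 and z = 2.128 at 0.0333:

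| Difference | At 0.017 | At 0.0333 | Gain (points) |
|---|---|---|---|
| 200 | 5.9% | 9.7% | 3.8 |
| 400 | 22.9% | 31.4% | 8.5 |
| 600 | 53.1% | 63.2% | 10.1 |
| 800 | 81.6% | 87.7% | 6.1 |

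At 80% power, moving from 0.0167 to 0.0333 is worth (2.394 + 0.842)²/(2.128 + 0.842)² = 1.19, or about 19% more participants in that comparison.

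**Power of the whole gated procedure, simulated:**

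| True effects | Comparison | Plan | Modified rule |
|---|---|---|---|
| 0/400/800 | 400 v 800 | 1.3% | 2.2% |
| 400/600/800 | 600 v 800 | 0.9% | 1.6% |
| 0/800/1000 | 800 v 1000 | 2.7% | 4.9% |
| 800/800/1200 | 800 v 1200 | 13.8% | 16.9% |
| 0/800/1200 | 800 v 1200 | 13.8% | 20.2% |
| 0/800/1400 | 800 v 1400 | 38.1% | 46.9% |
| 0/1200/1600 | 1200 v 1600 | 22.4% | 31.0% |
| 800/1200/1600 | 800 v 1200 | 13.9% | 23.8% |
| 800/1200/1600 | 1200 v 1600 | 22.4% | 34.6% |
| 800/1200/1600 | 800 v 1600 | 63.8% | 64.6% |

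A wider grid took arm effects from 0 to 2000 and counted pairs with both arms at 800 or more that differ by 200 to 800. There the gain ran from 0.5 to 15.8 points, with median 5.5 and middle half 2.8 to 8.4.

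**The case against.** The strongest reply is that nothing is wrong. The plan calls its rule conservative, says it allows for *up to* three comparisons, and fixes one level in advance. Its error claim holds: the simulated maximum is about 0.045, and the only excess in the bound is rounding (3 × 0.017 = 0.051). One threshold with matching 98.3% intervals is a legitimate choice. All of this stands, and it is why the point is an improvement and not a defect.

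The second reply concerns size. The only planning effect in the documents is 800 steps over control. If no arm exceeds that, the gain is about 1 point or less, because the gate then rarely leaves two arms that look far apart. This also stands.

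Three stronger readings are tempting, and the documents do not support them:
- *The flat level costs 6 to 12 points in general.* That range belongs to particular patterns with arms at 1200 to 1600 steps. Even there it is not universal: the widest pair in 800/1200/1600 gains under 1 point, and 800/800/1200 gains about 3.
- *A lone comparison can use the full 0.05.* It cannot. The arm that failed has already used 0.0167, and with one null arm and two equal strong arms the familywise error would be about 0.066.
- *The change makes phase 2 adequately powered.* It does not. In most of the patterns above power stays below 50% under either rule.

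What the replies do not remove is that, rounding aside, the modified rule is never less powerful in phase 2 and keeps the same stated error rate.

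**Conclusion.** The point holds as a low-cost efficiency gain. The plan's phase 2 rule controls familywise error but leaves part of the 0.05 unspent when exactly two arms succeed, or when one of three comparisons has been rejected.

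The gain cannot be given as one number, because the plan states no phase 2 effect. At 135 per arm and SD 2000 it is about 0 to 16 points per comparison: about 1 or less with no arm above 800 steps, about 2 to 3 for 0/800/1000 or 800/800/1200, and about 6 to 12 for patterns such as 0/800/1200 or the adjacent pairs of 800/1200/1600.

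The figures assume independent participants. Arms 3 and 4 work in groups of three, and correlation within groups would lower all the power figures.

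**What to change.** In sections 5.4 and 9, replace the phase 2 rule with: *If exactly two arms are successful, the single comparison is tested at two-sided 0.0333. If all three are successful, the smallest p-value is tested at 0.05/3; if it is rejected, the other two comparisons are tested at 0.05.*

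Write the phase 1 threshold as 0.05/3, so that the sum is exactly 0.05. Keep plain Bonferroni in phase 1 and do not change it to Holm: the 0.0333 relies on each phase 1 test being held to 0.05/3.

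The cost is two sentences, with no extra participants or data. The change should be made while the arms are still coded, which section 11.6.1 says they remain until analysis is complete. The downside is that fixed 98.3% intervals for phase 2 may disagree with the step-down test in borderline cases; the plan should say that the test governs.

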### *5.5 Key inclusion criteria*

1) Age 18 years or older; 2) ability to read and provide informed consent to participate in the study; 3) Self-reported body mass index (BMI) of 25 or greater. 4) Smartphone or tablet compatible with application for the wearable activity tracking device.

### *5.6 Key exclusion criteria*

1) Conditions that would make participation infeasible such as inability to provide informed consent, illiteracy or inability to speak, read, and write English; 2) conditions that would make participation unsafe such as pregnancy or being told by a physician not to exercise; 3) already enrolled in another study targeting physical activity; 4) any other medical conditions or reasons he or she is unable to participate in a physical activity study for 36 weeks.

## **6. Subject recruitment**

Recruitment will occur by email invitation to employees in the United States at Deloitte, a large consulting company.

## **7. Subject compensation**

All participants will receive \$25 to enroll in the study (defined as being randomized and starting the intervention), \$50 for completing the 24-week intervention and surveys, and \$50 for completing the entire 36-week study.

## **8. Study procedures**

### *8.1 Consent*

Upon recruitment, individuals who are interested in learning more about the study will be directed to the Way to Health web portal. Upon reaching the portal, potential participants will be asked to create an account and will then be informed of the details of the study, including its objectives, duration, requirements, and financial payments. If participants are still interested in participating, the Way to Health portal will take them through an automated online informed consent. The consent document will be divided into sections and potential participants will have to click a button to advance through each section. This is to help ensure that participants read the consent form thoroughly by breaking down the form into manageable blocks of text. Successive screens will explain the voluntary nature of the study, the risks and benefits of participation, alternatives to participation, and that participants can withdraw from the study at any time. On the final consent screen, potential participants who click a clearly delineated button stating that they agree to participate in the study will be considered to have consented to enroll. Participants will be provided with details regarding how to contact the research team via email or phone at any time if they subsequently wish to withdraw from the study. This contact information will remain easily accessible via the participants' individual Way to Health web portal dashboards throughout the study.

### *8.2 Procedures*

After providing informed consent, participants will complete an online questionnaire to determine their eligibility and complete the study surveys. Eligible participants will be mailed a wearable activity tracking device to wear a two week run-in period to collect a baseline step count.

Participants will select step goals and then be randomly assigned as described in the Study Design section.

We will obtain additional information about characteristics and behaviors of participants from the KBM Group, a data analytics firm. Participants will provide consent for the study team to send KBM Group their name and address using secure data transfer methods.

